9.1.2. Screening Phase

The screening assessments indicated in the [Time and Events Schedule](#) will occur within 2 weeks following evidence of newly documented HIV-1 infection.

The ICF must be signed before any study-specific procedures at the start of the screening period.

Only subjects complying with the selection criteria as specified in Section 4, Subject Population, will be included in the study. The investigator will provide detailed information about the study to the subject and will obtain written informed consent before each subject's study participation. Procedures indicated in the [Time and Events Schedule](#) will only be performed after the subject's written informed consent has been obtained. Relevant historical data obtained from the subject's medical records and/or subject interview will be captured.

Subjects meeting all of the inclusion criteria and none of the exclusion criteria will enter the open-label treatment phase.

9.1.3. Open-Label Treatment Phase

9.1.3.1. Main Study Period

All subjects must start dosing within 24 hours of the screening/baseline visit (Day 1).

Following initiation of treatment, a safety assessment will be made by the investigator at Day 3 +1 week (or as soon as the final screening/baseline laboratory report becomes available), and the ARV screening/baseline resistance data will be reviewed by the investigator at Week 4±7 days or sooner, depending on the availability of screening/baseline HIV genotypic drug resistance testing results from the central laboratory. The investigator will determine as to whether treatment should be discontinued, based on the stopping rules provided in Section 3.1.

Subjects will be treated for 48 weeks in the main study period and will return to the site for visits at Weeks 2, 4, 8, 12, 24, 36, and 48 (scheduled relative to the date of the baseline visit) and complete the procedures indicated in the [Time and Events Schedule](#). Subjects should be counseled regarding the importance of adherence, and be instructed to bring unused medication and empty packaging to the unit at each visit.

Subjects experiencing protocol-defined virologic failure (as defined in Section 3.1) will undergo genotypic and phenotypic resistance testing. In case resistance to study drugs is observed, the subject may be discontinued from the study at the investigator's discretion. Protocol-defined virologic failure is not considered a stopping rule.

9.1.3.2. Extension Period

Subjects who have completed the Week 48 visit will be given the opportunity to continue D/C/F/TAF treatment during an extension period until the D/C/F/TAF FDC tablet becomes commercially available and is reimbursed, or can be accessed through another source, or until the sponsor terminates clinical development. At Week 48 the investigator should dispense a sufficient supply of D/C/F/TAF to maintain continuity of care for the subject, however no more than 12 weeks of study medication should be dispensed. If a subject requires more than 12 weeks of study medication, the subject should return to the site for additional drug dispensation. During the extension period, subjects will have a study visit at the site once every 6 months, if applicable, and complete the procedures indicated in the [Time and Events Schedule](#), and additionally at the time of transition to commercial D/C/F/TAF, for final data collection.

Early Study Treatment Discontinuation (ESTD)

Subjects who prematurely discontinue study treatment during the open-label treatment period (ie, including the extension period) will be required to complete ESTD assessments as soon as possible but no later than 1 week of discontinuing study treatment.

For subjects who discontinue study treatment after Week 12 for any reason and have HIV-1 RNA ≥ 400 copies/mL at the last viral load measurement, the ESTD assessments will also include genotypic and phenotypic resistance testing. In case of early discontinuation, an HIV-1 resistance report will be forwarded to the subject's primary care provider to assist in the selection of a new ARV regimen.

30-Day Follow-up

In addition, a follow-up visit is required for any subject who has an ongoing adverse event or serious adverse event at the time of his/her last study visit. These subjects are required to return to the site 30 days (± 7 days) after completion of the last study-related visit (unless consent is withdrawn) and complete all procedures indicated in the [Time and Events Schedule](#).

End of Study

At the end of the study (or at ESTD), subjects will resume routine clinical care with their care provider who will transition them to an appropriate treatment regimen.

9.2. Efficacy Evaluations

9.2.1. Antiviral Efficacy and Immunologic Change

Blood samples for determination of plasma HIV-1 RNA viral load and immunologic parameters will be taken at the time points specified in the [Time and Events Schedule](#).

Plasma viral load will be measured using a validated assay at a central laboratory.

Immunologic change will be determined by changes in CD4⁺ cell count (absolute and %).

Changes in viral load, changes in CD4⁺ cell counts (either decreases or increases), or detected resistance will be part of the efficacy analysis and should not be reported as adverse events or serious adverse events.

9.2.2. Resistance Determinations

HIV-1 genotype/phenotype resistance testing will be performed at the time points specified in the [Time and Events Schedule](#).

Resistance testing at the screening/baseline visit (Day 1) will be performed utilizing the GenoSure Prime[®] assay. Resistance-associated mutations present at baseline will be reported and include mutations in the domain of PR, RT, and INI.

To investigate the emergence of resistance, the following subjects will be eligible for genotypic/phenotypic resistance testing (PhenoSense GT[®]):

- Any subject who experiences a protocol-defined virologic failure;
- Any subject who discontinues study treatment after Week 12 for any reason and has an HIV-1 RNA value ≥ 400 copies/mL at the last viral load measurement;
- Any subject who has persistent HIV-1 RNA ≥ 400 copies/mL past Week 24 but does not meet the definition of virologic failure.

Baseline phenotyping may be performed retrospectively on subjects with confirmed protocol-defined virologic failure if after virologic failure they showed evidence of reduced phenotypic susceptibility to any of the study drugs. Evaluations may be performed at other time points at the sponsor's discretion.

9.3. Pharmacokinetics

Plasma concentrations of DRV and COBI may be determined in subjects experiencing protocol-defined virologic failure, or subjects who have persistent HIV-1 RNA ≥ 400 copies/mL past Week 24 but do not meet the definition of virologic failure, using stored blood samples collected throughout the study, if deemed necessary.

9.4. Medical Resource Utilization and Health Economics

Medical resource utilization data will be collected in the eCRF by the investigator and study-site personnel. The following will be evaluated throughout the study as noted in the [Time and Events Schedule](#):

- Number and duration of hospitalizations.
- Number of outpatient visits, including type of visit (eg, general practitioner, specialist)
- Number of emergency room visits.
- Number and type of medications used (from the Concomitant Medication page of the eCRF).

Medical resource utilization will be classified as being either HIV-related or All-cause HRU as assessed by the investigator. The costs will be assigned to the type of medical resource utilization to calculate a per subject per month cost associated with the initiation and maintenance of ART.

Trends will be assessed over time throughout the study.

9.5. Adherence

Treatment adherence will be assessed by pill count and by subject self-report at the time points specified in the [Time and Events Schedule](#).

Subjects should be counseled regarding the importance of adherence, and be instructed to bring unused medication and empty packaging to the unit at each visit.

If non-adherence is identified during drug accountability the reasons for non-adherence will be captured in the eCRF.

9.6. Retention in Care

Retention in care will be described as the proportion of subjects who discontinue study treatment prior to Week 48 and remain in care after discontinuation (defined as having a documented office visit within 90 days of discontinuing the study drug). Subjects who withdraw consent will not be followed to assess retention in care.

9.7. Safety Evaluations

The study will include the following evaluations of safety and tolerability according to the time points provided in the [Time and Events Schedule](#): adverse event reporting, clinical laboratory tests (including biochemistry, hematology, urinalysis, and urine chemistry), vital signs, and physical examinations (complete or symptom-directed). These protocol procedures are described below. In addition to these measurements, guidelines for the management of toxicities are described in Section [9.8](#).

Any clinically relevant changes occurring during the study must be recorded on the Adverse Event section of the eCRF.

Clinical events and clinically significant laboratory abnormalities will be graded according to the Division of AIDS (DAIDS) Table for Grading the Severity of Adult and Pediatric Adverse Events located in [Attachment 2](#).

Any evaluations showing abnormal results at any time during the study will be followed until satisfactory clinical resolution or stabilization. All grade 3 and grade 4 laboratory abnormalities and all laboratory abnormalities resulting in an increase of 2 DAIDS grades from baseline will be followed until return to baseline or within 1 grade from baseline (ie, \leq grade 2) (see Section [9.8.1](#), General Guidance for the Management of Clinical Events and Laboratory Abnormalities).

Evaluations at the ESTD visit showing abnormal results indicating a possible causal relationship with the study treatment must be followed by the investigator (as often as deemed prudent) until

satisfactory clinical resolution or stabilization. Certain long-term adverse events of ART cannot be followed to resolution within the setting of this protocol; in these cases, follow-up will be the responsibility of the treating physician, which will be agreed upon with the sponsor's medical monitor.

Adverse Events

Adverse events will be reported by the subject (or, when appropriate, by a caregiver or surrogate) for the duration of the study. Adverse events will be followed by the investigator as specified in Section 12, Adverse Event Reporting.

Special attention will be paid to those subjects who discontinue the study for an adverse event, or who experience severe (grade 3) or potentially life-threatening (grade 4) adverse events, or a serious adverse events. For reported HIV events, further details will be recorded if these events are AIDS-defining illnesses (World Health Organization Clinical Staging of HIV/AIDS, located in Attachment 3). For subjects with specific adverse events, toxicity management should be done as described in Section 9.8, Toxicity Management.

Clinical Laboratory Tests

Blood samples for serum chemistry and hematology and a urine sample for urinalysis will be collected at predefined time points (see Time and Events Schedule).

All clinical laboratory testing will be performed by the central laboratory and results will be sent to the investigator. The investigator must review the laboratory results, document this review, and record any clinically relevant changes occurring during the study in the adverse event section of the eCRF. The laboratory reports must be filed with the source documents.

The central laboratory will send the investigator and sponsor an alert form whenever a grade 3 or grade 4 laboratory abnormality (see Attachment 2) is observed. In case a grade 3 or grade 4 laboratory abnormality occurs, a confirmatory test should be performed preferably within 72 hours after the results have become available, before study treatment interruption or discontinuation, unless such delay is not consistent with good medical practice.

If a grade 3 or grade 4 laboratory abnormality is well documented before the start of the study and not considered a safety concern by the investigator, a confirmatory retest is not mandatory. The following laboratory abnormalities do not warrant mandatory confirmation:

- Asymptomatic grade 3 or grade 4 glucose elevations in subjects with pre-existing diabetes.
- Asymptomatic grade 3 or grade 4 triglyceride or cholesterol elevations.

For more details on the management of grade 3 and 4 laboratory toxicities that occur during the open-label treatment phase, see Section 9.8.1, General Guidance for the Management of Clinical Events and Laboratory Abnormalities, and Attachment 4. Please note that this attachment does not apply to screening/baseline eGFR, AST, ALT, and lipase, and does also not apply to the allowed retesting of abnormal screening/baseline eGFR, AST, ALT, and lipase values (see Section 3.1).

The following tests will be performed by the central laboratory:

- Hematology Panel*

-hemoglobin	-platelet count
-hematocrit	-CD4 ⁺ cell count
-absolute neutrophil count	-CD8 ⁺ cell count
-white blood cell count (WBC) with differential	-CD4 ⁺ CD8 ⁺ ratio
-red blood cell count (RBC)	

* Peripheral blood mononuclear cells (PBMCs) will be isolated from whole blood at the central laboratory at predefined time points (see [Time and Events Schedule](#)), and stored for future analysis if needed.

- Serum Chemistry Panel

-glucose	-chloride
-calcium	-phosphate
-calcium corrected for albumin	-blood urea nitrogen (BUN)
-albumin	-serum creatinine, including calculated eGFR
-total protein	-alkaline phosphatase (ALP)
-sodium	-AST
-potassium	-ALT
-bicarbonate (HCO ₃)	-bilirubin (total, direct, indirect)

- Urinalysis (dipstick)

-specific gravity	-ketones
-pH	-bilirubin
-glucose	-urobilinogen
-protein	-nitrite
-blood	-leukocyte esterase

If dipstick results are abnormal, the sediment will be examined microscopically.

In the microscopic examination, observations other than the presence of WBCs, RBCs, and casts may also be reported by the laboratory.

- Urine chemistry panel (only in the setting of a suspected renal adverse event; quantitative)

-creatinine	-glucose
-sodium	-protein
-phosphate	-albumin

Additional clinical laboratory assessments to be performed are as follows:

- Hepatitis C virus (HCV) testing (HCV antibodies [Ab] and HCV RNA level [only if HCV Ab+]) and hepatitis B virus (HBV) testing (anti-hepatitis B core [HBc], anti-hepatitis B surface [HBs], hepatitis B surface antigen [HBsAg]) (at screening only). Whenever clinically relevant, the investigator can request additional tests at other visits.

- A urine pregnancy test will be performed at screening for all female subjects of childbearing potential. A serum human chorionic gonadotropin pregnancy test will be assessed at a central laboratory, but the results are not required for enrollment. A urine pregnancy test will be performed at subsequent study visits as outlined in the [Time and Events Schedule](#). Positive urine pregnancy tests will be confirmed with a serum pregnancy test. The results of the serum and urine pregnancy tests should be recorded in the eCRF and in the subject's medical records.
- Amylase (pancreatic) (only at screening and in case of suspected pancreatitis during the study period)
- Lipase (only at screening and reflex if amylase elevated)
- In case of rash, safety blood samples need to be taken and are to be processed by the central laboratory. For details on rash management, see Section [9.8.2](#), Cutaneous Events/Rash.

Vital Signs (Including Height and Weight)

Blood pressure (systolic and diastolic) and pulse/heart rate measurements (supine after at least 5 minutes rest) should be preceded by at least 5 minutes of rest in a quiet setting without distractions (eg, television, cell phones). Blood pressure and pulse/heart rate measurements will be assessed with a completely automated device. Manual techniques will be used only if an automated device is not available.

To obtain the actual body weight, subjects should be weighed lightly clothed.

Height should be measured barefooted at the screening visit.

Any clinically relevant findings at screening and changes occurring during the study must be recorded in the Adverse Event section of the eCRF.

Physical Examination

Complete physical examinations, or symptom-directed examinations (physical examinations for which symptoms have been reported by the subject) as needed, will take place at the time points in the [Time and Events Schedule](#).

Complete physical examinations include skin, eyes, ears, nose, and throat, head, neck, and thyroid, heart, lung, chest (incl. breasts), abdomen, genitalia, anorectal, lymph nodes, musculoskeletal, and neurological. Urogenital/anorectal examination will be performed at the discretion of the investigator if clinically relevant. Subjects should be undressed during the complete physical examinations, which should be performed by a licensed medical doctor, physician's assistant or nurse practitioner in accordance with local guidelines.

Any clinically relevant findings at screening and changes occurring during the study must be recorded in the Adverse Event section of the eCRF.

Patient-reported Outcomes

Patient-reported outcomes will be assessed at the time points indicated in the [Time and Events Schedule](#) utilizing the HIVTSQs. The HIVTSQs should be completed before all other study-related procedures planned during these visits to prevent influencing subject perceptions.

9.8. Toxicity Management

The toxicity management guidelines in this section are applicable throughout the entire study starting from when the subject starts study medication through the 48-week main study period and the extension period.

General guidance for the management of toxicities is provided in Section 9.8.1. Guidance for specific toxicities is provided in Sections 9.8.2 through 9.8.8. In addition, see Section 9.7, Safety Evaluations, and Section 12, Adverse Event Reporting, for details on procedures concerning the measurement and reporting of clinically relevant abnormalities and toxicities.

Questions regarding toxicity management should be directed to the sponsor's medical monitor.

9.8.1. General Guidance for the Management of Clinical Events and Laboratory Abnormalities

Grade 1 and 2

Continue study treatment at the discretion of the investigator.

Grade 3

- For a grade 3 clinical event or clinically relevant laboratory abnormality, study treatment may be continued if the event is considered to be unrelated to study treatment.
- For a grade 3 clinical event, or clinically relevant laboratory abnormality confirmed by repeat testing (see Section 9.7), that is considered related to study treatment, study treatment should be withheld until the toxicity returns to baseline or within 1 grade from baseline, ie, \leq grade 2.
- Mandatory confirmation is not warranted for asymptomatic grade 3 glucose elevations in subjects with pre-existing diabetes, and for asymptomatic grade 3 triglyceride or cholesterol elevations.
- If a laboratory abnormality recurs to \geq grade 3 following rechallenge with study treatment and is considered to be related to study treatment, study treatment should be permanently discontinued and the subject managed according to local practice. Recurrence of laboratory abnormalities considered unrelated may not require permanent discontinuation.

Grade 4

- For a grade 4 clinical event or clinically relevant laboratory abnormality confirmed by repeat testing (see Section 9.7), that is considered related to study treatment, study treatment should be permanently discontinued and the subject managed according to local practice. The subject should be followed as clinically indicated until the laboratory abnormality returns to baseline or is otherwise explained, whichever occurs first. A clinically relevant grade 4 laboratory

abnormality that is not confirmed upon repeat testing should be managed according to the algorithm for the new toxicity grade.

- Mandatory confirmation is not warranted for asymptomatic grade 4 glucose elevations in subjects with pre-existing diabetes, and for asymptomatic grade 4 triglyceride or cholesterol elevations.
- Study treatment may be continued without dose interruption for a clinically nonrelevant grade 4 laboratory abnormalities (eg, grade 4 creatine phosphokinase after strenuous exercise, or triglyceride elevation that is nonfasting or that can be medically managed), or a clinical event considered unrelated to study treatment.

A schematic overview of these guidelines is provided in [Attachment 4](#) for clinically relevant laboratory toxicities that occur while on treatment. Please note that this attachment does not apply to screening/baseline eGFR, AST, ALT, and lipase, and does also not apply to the allowed retesting of abnormal screening/baseline eGFR, AST, ALT, and lipase values (see Section [3.1](#)).

9.8.2. Cutaneous Events/Rash

Darunavir is a sulfonamide. Subjects who previously experienced sulfonamide allergy will be allowed to enter the study. To date, no potential for cross-sensitivity between drugs in the sulfonamide class and DRV has been identified.

Cutaneous events/rash should be captured in the Adverse Event section of the eCRF.

Management of cutaneous events/rash will be at the discretion of the investigator, taking into account the following protocol procedures (see also [Table 1](#)), and should follow generally accepted medical standards. Cetirizine, levocetirizine, topical corticosteroids, and antipruritic agents will be allowed at the investigator's discretion for treatment of all grades of rashes.

Grade 1 and 2 Cutaneous Reaction/Rash

A grade 1 cutaneous reaction/rash is defined as localized rash.

A grade 2 cutaneous reaction/rash is defined as diffuse rash or target lesions.

Subjects experiencing a grade 1 or 2 rash or cutaneous event may continue treatment, or have their study treatment interrupted at the investigator's discretion. Safety sampling (processed by the central laboratory) at the time of the rash and clinical follow-up for these adverse events will be at the discretion of the investigator; however, close clinical follow-up is recommended to monitor for any progression of the adverse event.

Grade 3 and 4 Cutaneous Reaction/Rash

A grade 3 cutaneous reaction/rash is defined as:

- Diffuse rash with vesicles or limited number of bullae or superficial ulceration of mucous membrane limited to 1 site.

For the purpose of this study, the sponsor considers qualifying as a grade 3 rash:

- Cutaneous reaction/rash with at least 1 of the following:
 - elevations of ALT/AST $>2\times$ baseline but $\geq 5\times$ ULN
 - fever $\geq 38^{\circ}\text{C}$ or 100°F
 - serum sickness-like reaction
 - eosinophil count $>1,000/\text{mm}^3$
- The syndromes of DRESS and AGEP

A grade 4 cutaneous reaction/rash is defined as:

- Extensive or generalized bullous lesions
- Stevens-Johnson syndrome (SJS)
- Ulceration of mucous membrane involving at least 2 distinct mucosal sites
- Toxic epidermal necrolysis (TEN)

Subjects experiencing a grade 3 or 4 rash or cutaneous event must have their study treatment discontinued. Referral to a dermatologist and biopsy are required for these events preferably within 24 hours after the site becomes aware of the cutaneous event/rash.

Safety testing (to be processed by the central laboratory) of the following parameters is required to determine possible liver or systemic abnormalities: ALT, AST, bilirubin (total, direct and indirect), creatinine and a hematology profile. Close clinical follow-up and appropriate medical intervention should be instituted for these events; daily follow-up is recommended for 5 days from the onset of the event to monitor for progression of the event and weekly afterwards as long as grade 3 or 4 rash is present. Once grade 3 or 4 rash has resolved to \leq grade 2 rash, follow-up should be done according to the instructions for grade 1 or 2 rash.

Table 1: Summary of Cutaneous Reaction/Rash Follow-up

DAIDS Toxicity Grade	Definitions	Investigator Action
Grade 1	Localized rash	Subject may continue study treatment
Grade 2	Diffuse rash Target lesions	Subject may continue study treatment
Grade 3	Diffuse rash with vesicles or limited number of bullae Superficial ulcerations of mucous membrane limited to 1 site For the purpose of this protocol, the sponsor considers qualifying as a grade 3 rash the following: Cutaneous reaction/rash with at least 1 of the following: - Elevations in ALT and/or AST (>2× baseline but ≥5× ULN) - Fever ≥38°C or 100 F - Serum sickness-like reaction - Eosinophils >1,000/mm ³ DRESS and AGEP	Permanently discontinue study treatment Referral to a dermatologist and biopsy, preferably within 24 hours after the site becomes aware of the cutaneous event/rash Laboratory assessments need to be performed
Grade 4	Extensive or generalized bullous lesions SJS Ulceration of mucous membrane involving at least 2 distinct mucosal sites TEN	Permanently discontinue study treatment Referral to a dermatologist and biopsy, preferably within 24 hours after the site becomes aware of the cutaneous event/rash Laboratory assessments need to be performed

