Retesting of abnormal screening/baseline safety laboratory values noted above will be allowed once. Retesting will take place during an unscheduled visit.

The investigator will review the ARV screening/baseline resistance data at Week 4 ± 7 days or sooner, depending on the availability of the screening/baseline HIV genotypic drug resistance testing results from the central laboratory. Subjects who do not show full sensitivity to all drugs in the FDC study regimen according to the susceptibility assessment in the GenoSure Prime[®] report will be contacted to return to the study site for ESTD. Subjects with identified resistance to lamivudine/FTC, attributed to the presence of the M184I/V mutation alone will be permitted to remain in the study.

Subjects will be treated for 48 weeks in the main study period and will return to the site for visits at Weeks 2, 4, 8, 12, 24, 36, and 48. Assessment of drug accountability and reasons for non-adherence, and recording of concomitant therapies, adverse events, vital signs (including the subject's body weight), and physical examinations (complete or symptom-directed) will be performed at each visit from baseline onwards. Laboratory evaluations for efficacy and safety (HIV-1 viral load, biochemistry, hematology, and urinalysis) will be performed at all study visits. CD4⁺/CD8⁺ cell count will be assessed at Weeks 4, 8, 12, 24, 36, and 48. Patient-reported outcome (PRO) measures will be assessed at Weeks 4, 24, and 48 using the validated 10-item HIVTSQs (Version 2006)¹² ([Attachment 7](#)). Medical resource utilization data will be collected from all subjects throughout the main study period.

Subjects who are on study drug and who experience a protocol-defined virologic failure (see below) will undergo genotypic and phenotypic resistance testing, preferably at the time of the confirmed virologic failure visit if the HIV-1 RNA is ≥ 400 copies/mL. If resistance testing is not able to be performed at the time of confirmed virologic failure, resistance testing may be

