Subjects who have completed the Week 48 visit will be given the opportunity to continue D/C/F/TAF treatment during an extension period until the D/C/F/TAF FDC tablet becomes commercially available and is reimbursed, or can be accessed through another source, or until the sponsor terminates clinical development. At Week 48 the investigator should dispense a sufficient supply of D/C/F/TAF to maintain continuity of care for the subject, however no more

than 12 weeks of study medication should be dispensed. If a subject requires more than 12 weeks of study medication, the subject should return to the site for additional drug dispensation.

During the extension period, subjects will have a study visit at the site once every 6 months, if applicable, and complete the procedures indicated in the [Time and Events Schedule](#), and additionally at the time of transition to commercial D/C/F/TAF, for final data collection.

At the end of the study (or at ESTD), subjects will resume routine clinical care with their care provider who will determine the future care of that subject. In anticipation of transitioning the subject to routine clinical care at the end of the study (or early discontinuation), the investigator should take steps to ensure a smooth transition (ie, secure insurance etc.) well in advance of the final study visit, so that the subjects' ART is not interrupted.

For those subjects discontinuing therapy before Week 48, the investigator will be asked to monitor the subject's retention in care defined as having one documented clinic visit within 90 days of discontinuing the study treatment (unless consent is withdrawn).

The end of the study is defined as completion of the last data collection visit for the last subject participating in the study. For the purpose of the primary analysis, a subject will be considered to have completed the study if data collection as required per protocol through the complete course of 48 weeks of ART has been completed.

An interim analysis will be conducted after the last subject enrolled has been assessed for safety at Day 3, and for resistance stopping rules at Week 4.

The primary analysis of this study will be performed once all subjects have completed the Week 48 visit and the 30-day follow-up visit (if applicable), or discontinued earlier.

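### Sections 9.7 and 9.8.2 conflict on blood sampling for rash, and 9.8.2 lets a site grade a rash without the laboratory values that can make it grade 3

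*Protocol*

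**What the plan says.** Section 9.7, in its list of additional laboratory assessments, states: "In case of rash, safety blood samples need to be taken and are to be processed by the central laboratory". No grade is mentioned. The entry then refers the reader to Section 9.8.2 for how rash is managed.

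Section 9.8.2 grades rash first by appearance: localized is grade 1; diffuse, or with target lesions, is grade 2. For both, drug may be continued or interrupted as the investigator judges, and sampling is likewise left to the investigator: "Safety sampling (processed by the central laboratory) at the time of the rash and clinical follow-up for these adverse events will be at the discretion".

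The section then adds the sponsor's own route to grade 3. A rash qualifies if it comes with any one of four features: an ALT/AST elevation, fever, a serum sickness-like reaction, or a raised eosinophil count, given in Table 1 as "Eosinophils >1,000/mm"3. DRESS and AGEP also count as grade 3. At grade 3 or 4 the drug is stopped (permanently, according to Table 1), and dermatology referral and biopsy are required.

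Mandatory laboratory work in 9.8.2 belongs to grades 3 and 4 only: "Safety testing (to be processed by the central laboratory) of the following parameters is required to determine possible liver or systemic abnormalities". In Table 1 the instruction "Laboratory assessments need to be performed" stands in the grade 3 and grade 4 rows and in no other.

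**The concern.** There are two faults. The first is between sections: 9.7 makes sampling mandatory for rash of any grade, and 9.8.2 makes it optional for grades 1 and 2. Sites can follow either and believe that they comply.

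The second lies inside 9.8.2 and remains whichever section governs. The grade decides whether blood must be drawn, yet two of the four added grade 3 criteria can be seen only in blood. A rash that looks mild and is not sampled is handled as one where treatment may continue, even if its laboratory values would make it grade 3.

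The protocol gives reasons to take this seriously. Section 1.2 lists rash among the most common grade 2 or higher reactions to ritonavir-boosted darunavir in an earlier Phase 3 trial. Section 1.2.1 lists DRESS, AGEP and TEN among postmarketing reactions. Section 9.8.2 admits subjects with previous sulfonamide allergy. Section 10.2 lists unacceptable toxicity as defined in 9.8 among the reasons for which treatment must stop. The counts of grade 3 and 4 adverse events, and of discontinuations due to adverse events, would also depend in part on which section each site follows.

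**Working it through.** The protocol gives no figure to reproduce here. The check is a comparison of its instructions, followed by the visit spacing and a labelled illustration.

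**1. The instructions side by side**

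| Question | Section 9.7 | Section 9.8.2, grade 1–2 | Section 9.8.2, grade 3–4 |
|---|---|---|---|
| Blood sample? | Required for any rash | Investigator's choice | Required |
| Study drug | Refers to 9.8.2 | May continue or be interrupted | Stopped permanently |

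**2. Which added grade 3 criteria need blood?** ALT/AST and eosinophils do; fever and a serum sickness-like reaction can be recognized clinically. So 2 of 4 need a sample.

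**3. An example.** A subject has an afebrile, diffuse rash, with ALT at 6×ULN from a normal baseline. A normal baseline is at most 1×ULN, so 6×ULN is more than twice baseline and at least 5×ULN; the criterion as printed is met. If sampled, the rash is grade 3 and drug stops for good. If not sampled, it is grade 2 and drug may continue. The same holds with normal ALT and eosinophils of 1,200/mm3.

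**4. Would another safeguard catch it?**
- *Laboratory alert.* Section 9.7 says: "The central laboratory will send the investigator and sponsor an alert form whenever a grade 3 or grade 4 laboratory abnormality" is observed. This needs a sample. It would flag ALT at 6×ULN (grade 3 in Attachment 2), but Attachment 2 has no eosinophil row, so an eosinophil count would raise no alert.
- *Scheduled draws.* Section 3.1 says that subjects "will return to the site for visits at Weeks 2, 4, 8, 12, 24, 36, and 48". From Day 1 the gaps are 2, 2, 4, 4, 12, 12 and 12 weeks. The three long gaps cover 12 + 12 + 12 = 36 of 48 weeks, and 36/48 = 75%. In the extension, "subjects will have a study visit at the site once every 6 months". The 75% is calendar time, not a share of rash risk: up to Week 12 the draws are 2 to 4 weeks apart. No scheduled draw is tied to the onset of a rash.

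**5. Illustration of frequency (assumed inputs).** The protocol gives neither the number of rashes expected in this study nor the share that would meet a laboratory criterion. Assume n rashes that look grade 1–2 among about 100 subjects, each meeting a laboratory criterion with probability p. The expected number is n × p, and the chance of at least one is 1 − (1 − p)^n.

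| n | p | Expected | Chance of at least one |
|---|---|---|---|
| 5 | 0.02 | 0.1 | 1 − 0.98^5 = 9.6% |
| 10 | 0.05 | 0.5 | 1 − 0.95^10 = 40.1% |
| 15 | 0.10 | 1.5 | 1 − 0.90^15 = 79.4% |

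For the given inputs these count rashes that meet a criterion. Fewer would be missed, because some sites would sample anyway. One subject in 100 is 1 percentage point.

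**The case against.** The best defence is that 9.7 holds a one-line entry in a list of tests and sends the reader to 9.8.2, so the specific, graded rule governs. A site that samples every rash also satisfies both sections. This softens the conflict between sections but leaves the circular grading within 9.8.2.

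Next, safeguards exist. Unscheduled visits and samples are allowed (Sections 3.1 and 9.1.1), rash care must meet accepted medical standards, close follow-up is advised for mild rash, and investigators must review every laboratory result, so eosinophils in a drawn sample would be seen without an alert. This is fair, and it narrows the gap to a rash that a clinician examined and chose not to sample. But either a safeguard needs a sample that 9.8.2 does not require, or it supplies no laboratory value.

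Third, the frequency range reflects only its assumed inputs. That is right, and the conclusion does not use it.

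Fourth, the ALT/AST criterion is oddly worded: it joins more than twice baseline to at least 5×ULN with a conjunction that normally introduces an upper limit. The intended threshold may differ from the printed one. The eosinophil criterion has no such doubt, so the point stands without the ALT example.

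Fifth, sampling every rash could force permanent discontinuation for a trivial rash in a subject with pre-existing eosinophilia, since that criterion has no baseline or relatedness condition. This is a real consequence, but of the sponsor's existing grade 3 rule; sampling only lets the rule operate. The opposite repair, limiting the 9.7 entry to grades 3 and 4, would reconcile the sections but keep the circular grading.

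**Conclusion.** The concern holds: the text is wrong as written. Sections 9.7 and 9.8.2 give different sampling rules for mild rash, and 9.8.2 by itself allows a rash to be graded without two of the four added criteria that can make it grade 3. A site can follow 9.8.2 exactly and leave on drug a subject who meets the sponsor's definition for permanent discontinuation.

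A missed case is possible, not certain, and its frequency cannot be taken from the protocol. The affected endpoints are descriptive, and each reclassified subject moves them by about 1 percentage point at the target of about 100. The conclusion rests on the wording alone. The change should be made for subject safety and for consistent grading across sites.

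**What to change.** Amend Section 9.8.2 and the grade 1 and 2 rows of Table 1 to agree with 9.7. For every rash, draw ALT, AST and hematology with differential at the time of the rash. State that a grade based on appearance is provisional and becomes final when those results are available. Until then, keep the existing discretion to continue or interrupt drug.

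The cost is a few lines of text and two table rows in the next amendment, and a few unscheduled samples that 9.7 already requires. Both panels are already run centrally. Some rashes may be reclassified to grade 3 and lead to discontinuation, which is what the sponsor's definition intends.
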